3.2 Clinical Study Design

This is a FIH, double-blind, parallel-group, randomised, placebo-controlled study designed to evaluate the safety, tolerability, PK and PD of single and multiple ascending oral doses of GS-248 in healthy subjects. In addition, an exploratory comparison of the PD effects between celecoxib and GS-248 will be performed.

Study GS-1001 include three parts: Part I (SAD), Part II (MAD) and Part IV (celecoxib). Part III (SSc patient) in this study was cancelled.

Part I (single ascending dose [SAD]): safety, tolerability, PK and PD of single ascending oral doses of GS-248 in healthy male and female subjects.

Part II (multiple ascending dose [MAD]): safety, tolerability, PK and PD of multiple ascending oral doses of GS-248 in healthy male and female subjects during 10 days administration.

Part III (SSc patients): cancelled.

Part IV (celecoxib): PD of multiple oral doses of celecoxib (200 mg BID) in healthy males and females during 10 days administration.

3.3 Statistical Hypotheses

No statistical hypotheses have been made in any of the study parts.

3.4 Number of Subjects

The total number of subjects included in the study (Part I, Part II and Part IV) were 80.

- Part I (SAD): 48 subjects were randomised and dosed (6 cohorts, each of 8 subjects with 6 subjects receiving GS-248 (1mg, 5mg, 8mg, 40mg, 100mg and 300mg) and 2 receiving placebo).
- Part II (MAD): 24 subjects were randomised and dosed (3 cohorts, each of 8 subjects with 6 subjects receiving GS-248 (20mg, 60mg and 180mg) and 2 receiving placebo).
- Part III in the study was cancelled.
- Part IV (celecoxib): 8 subjects were randomised and dosed (1 cohort with 8 subjects receiving 200mg celecoxib BID).

3.5 Methods of Assigning Subject to IMP

See section 3.4

3.6 Blinding

Part I (SAD) and Part II (MAD) were conducted in double-blinded fashion and the allocation of treatments were not disclosed until clean file was declared, and the database were locked for each part. GS-248 and the placebo are identical in appearance.

Part IV (celecoxib) was a non-placebo controlled, non-randomised and open study.

4 STATISTICAL AND ANALYTICAL PLANS

4.1 Sample Size Determination

No formal sample size calculations have been performed for any part in this study. The proposed sample size is considered sufficient to provide adequate information for the study objective.

4.2 Definition of Analysis Sets

Safety Analysis Set

Not applicable.

Full Analysis Set

The Full Analysis Set (FAS) of each part will consist of all subjects/patients who have been randomised and received at least one dose of IMP and who have at least one post-baseline assessment of efficacy data.

Per Protocol Analysis Set

Not applicable.

PK Analysis Set

Not applicable.

Use of analysis set

The FAS population will be used for all analyses presented in this SAP.

Safety analysis set and Per protocol analysis set (PPS) will not be used in any part or in any analysis.

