17.3 Analysis data sets

17.3.1 *Safety analysis set*

The safety analysis set of each part will consist of all subjects/patients who have been randomised and received at least one dose of IMP.

17.3.2 *Full analysis set*

The Full Analysis Set (FAS) of each part will consist of all subjects/patients who have been randomised and received at least one dose of IMP and who has at least one post-baseline assessment of efficacy data.

17.3.3 *Per protocol set*

The Per Protocol Set (PPS) of each part will consist of all subjects who have been randomised and completed the study without any major protocol deviations that are judged to compromise the analysis of the data. All protocol violations will be judged as major or minor prior to database lock.

17.3.4 *PK analysis set*

The PK analysis set will consist of all subjects who received at least one dose of the study drug and provided evaluable plasma concentration data and who have no AEs or protocol deviations judged to affect the PK analysis.

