7.1 Primary Endpoint(s) Analysis

Definition of endpoint(s)

The primary endpoints have been described in the previous SAP's, GS-1001SAP_v.10_11DEC2019- SAD, GS-1001SAP_v.1.0_13FEB2020- MAD and GS-1001SAP_v.10_27FEB2020- Part IV. The tables for Part II (MAD) and Part IV (celecoxib) will be combined.

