CLINICAL TRIAL CONSULTANTS AB Study Code: GS-1001

Table 14.2.1.1. Overview of adverse events ([analysis set])

	GS-248 20 mg (N=X)		GS-248 60 mg (N=X)		GS-248 180 mg (N=X)		[All GS-248] (N=X)		PLACEBO (N=X)		[All GS-248 and PLACEBO] (N=X)		celecoxib (N=X)	
	n(%)	m	n(%)	m	n(%)	m	n(%)	m	n(%)	m	n(%)	m	n(%)	m
Any AE	x(x.x%)	x	x(x.x%)	x	x(x.x%)	x	x(x.x%)	x	x(x.x%)	x	x(x.x%)	x	x(x.x%)	x
Any SAE	x(x.x%)	x	x(x.x%)	x	x(x.x%)	x	x(x.x%)	x	x(x.x%)	x	x(x.x%)	x	x(x.x%)	x
Any AE leading to withdrawal	x(x.x%)	x	x(x.x%)	x	x(x.x%)	x	x(x.x%)	x	x(x.x%)	x	x(x.x%)	x	x(x.x%)	x
Any AE leading to death	x(x.x%)	x	x(x.x%)	x	x(x.x%)	x	x(x.x%)	x	x(x.x%)	x	x(x.x%)	x	x(x.x%)	x
Causality														
Possibly Related	x(x.x%)	x	x(x.x%)	x	x(x.x%)	x	x(x.x%)	x	x(x.x%)	x	x(x.x%)	x	x(x.x%)	x
Probably Related	x(x.x%)	x	x(x.x%)	x	x(x.x%)	x	x(x.x%)	x	x(x.x%)	x	x(x.x%)	x	x(x.x%)	x
Unlikely Related	x(x.x%)	x	x(x.x%)	x	x(x.x%)	x	x(x.x%)	x	x(x.x%)	x	x(x.x%)	x	x(x.x%)	x
Severity														
Mild	x(x.x%)	x	x(x.x%)	x	x(x.x%)	x	x(x.x%)	x	x(x.x%)	x	x(x.x%)	x	x(x.x%)	x
Moderate	x(x.x%)	x	x(x.x%)	x	x(x.x%)	x	x(x.x%)	x	x(x.x%)	x	x(x.x%)	x	x(x.x%)	x
Severe	x(x.x%)	x	x(x.x%)	x	x(x.x%)	x	x(x.x%)	x	x(x.x%)	x	x(x.x%)	x	x(x.x%)	x
Life-threatening	x(x.x%)	x	x(x.x%)	x	x(x.x%)	x	x(x.x%)	x	x(x.x%)	x	x(x.x%)	x	x(x.x%)	x
Death	x(x.x%)	x	x(x.x%)	x	x(x.x%)	x	x(x.x%)	x	x(x.x%)	x	x(x.x%)	x	x(x.x%)	x

n, number of subjects; m, number of events

Percentages are based on the number of subjects in the treatment period included in the [analysis set].

Adverse events that occurred during screening are omitted from summary.

[STUDYID] Overview of adverse events, [analysis set], SAS program: ae_summary_tables.sas. Run by: [USERNAME], [USER EMAIL] [TIMESTAMP]

14.2.1.1: FAS

STATISTICAL ANALYSIS PLAN

Protocol Version No: Final Version 2.0, 29MAY2019

CTC Project No: 225-45.2018

CLINICAL TRIAL CONSULTANTS AB Study Code: GS-1001

Table 14.2.1.2. Adverse events by system organ class and preferred term ([analysis set])

System organ class Preferred term	GS-248 20 mg (N=X)		GS-248 60 mg (N=X)		GS-248 180 mg (N=X)		[All GS-248] (N=X)		PLACEBO (N=X)		[All GS-248 and PLACEBO] (N=X)		celecoxib (N=X)	
	n(%)	m	n(%)	m	n(%)	m	n(%)	m	n(%)	m	n(%)	m	n(%)	m
Total	x(x.x%)	x	x(x.x%)	x	x(x.x%)	x	x(x.x%)	x	x(x.x%)	x	x(x.x%)	x	x(x.x%)	x
SOC 1s	x(x.x%)	x	x(x.x%)	x	x(x.x%)	x	x(x.x%)	x	x(x.x%)	x	x(x.x%)	x	x(x.x%)	x
SOC 1 PT 1	x(x.x%)	x	x(x.x%)	x	x(x.x%)	x	x(x.x%)	x	x(x.x%)	x	x(x.x%)	x	x(x.x%)	x

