Protocol Version No: Final Version 2.0, 29MAY2019

CTC Project No: 225-45.2018

CLINICAL TRIAL CONSULTANTS AB Study Code: GS-1001

Listing 16.2.1. Discontinued subjects (All subjects)

Listing 16.2.2. Protocol deviations (All subjects)

Listing 16.2.3.1 Subject excluded from Per protocol set (All subjects)

Listing 16.2.3.2 Population definitions (All subjects)

Listing 16.2.3.3 Non-eligible subjects (All subjects)

Listing 16.2.4.1. Demography (Full analysis set)

Listing 16.2.4.2. Medical history (Full analysis set)

Listing 16.2.4.3 Adverse events as screening, part 1 (Full analysis set)

Listing 16.2.4.4 Adverse events as screening, part 2 (Full analysis set)

Listing 16.2.5.1 Prior and concomitant medications (Full analysis set)

Listing 16.2.5.2. Exposure (Full analysis set)

Listing 16.2.6.1. Adverse events, part 1 (Full analysis set)

STATISTICAL ANALYSIS PLAN

Protocol Version No: Final Version 2.0, 29MAY2019

CTC Project No: 225-45.2018

CLINICAL TRIAL CONSULTANTS AB Study Code: GS-1001

Listing 16.2.6.2. Adverse events, part 2 (Full analysis set)

Listing 16.2.6.3. Serious adverse events, part 1 (Full analysis set)

Listing 16.2.6.4. Serious adverse events, part 2 (Full analysis set)

Listing 16.2.6.5. Serious adverse events, seriousness criteria (Full analysis set)

Listing 16.2.7. ECG measurements (Full analysis set)

Listing 16.2.8. Vital signs (Full analysis set)

Listing 16.2.9.1 Laboratory values (Full analysis set)

Listing 16.2.9.2 Abnormal laboratory values (Full analysis set)

Listing 16.2.9. Physical examinations (Full analysis set)

Listing 16.2.10.1. GS-248 concentration (Full analysis set)

Listing 16.2.10.3. Pharmacokinetic parameters of GS-248 (Full analysis set)

Listing 16.2.10.5. PGE2 levels in WBA (Full analysis set)

STATISTICAL ANALYSIS PLAN

Protocol Version No: Final Version 2.0, 29MAY2019

CTC Project No: 225-45.2018

CLINICAL TRIAL CONSULTANTS AB Study Code: GS-1001

Listing 16.2.11.1. AA metabolites in urine ([analysis set])

Listing 16.2.11.2. ADMA in plasma ([analysis set])

Listing 16.2.11.3. L-Arg in plasma ([analysis set])

Listing 16.2.11.4. Biomarkers and GS-248 metabolites ([analysis set])

Listing 16.2.12. Disposition (All subjects)

Listing 16.2.13. Subject visits (All subjects)

Listing 16.2.14. Subject elements (All subjects)

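### The combined MAD and celecoxib safety outputs use a full analysis set that requires an undefined efficacy value, and the protocol's safety set is dropped without being listed as a change

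*SAP*

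**What the plan says.** Protocol 17.3.1 gives the safety set: "The safety analysis set of each part will consist of all subjects/patients who have been randomised and received at least one dose of IMP". Protocol 17.3.2 gives a narrower FAS, which also needs a subject "who has at least one post-baseline assessment of efficacy data". Protocol 17.5, on the primary endpoints, does not name the set for the safety tables.

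SAP 4.2 keeps the FAS definition (randomised, "received at least one dose of IMP and who have at least one post-baseline assessment of efficacy data"), marks the safety set as not applicable, and then fixes the use of sets: "The FAS population will be used for all analyses presented in this SAP" and "Safety analysis set and Per protocol analysis set (PPS) will not be used in any part or in any analysis".

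Other parts of the SAP carry this rule into the primary safety outputs:

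- SAP 2 places the combined MAD and Part IV descriptive tables on the FAS.
- SAP 7.1 says of the primary endpoints: "The tables for Part II (MAD) and Part IV (celecoxib) will be combined".
- The shell for Table 14.2.1.1 (AE overview) is tagged FAS, and its footnote takes percentages from the subjects in the analysis set. The other safety shells have a placeholder, which SAP 2 and 4.2 resolve to the FAS.
- All the AE, SAE, ECG, vital-sign, laboratory and physical-examination listings are titled as FAS.

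SAP 8, the list of changes from the protocol, has eight entries. None concerns an analysis set.

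**The concern.** Safety denominators should depend on exposure alone. Here they also depend on an assessment that has nothing to do with safety and that the documents do not identify. Someone programming the population flag would have to guess what efficacy data means, because every endpoint is safety, PK or exploratory PD.

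The subject most exposed to exclusion is one who is dosed and leaves very early, and an AE is one possible reason for leaving. Losing such a subject would remove the event from AE incidence and, if the listing titles are followed, from the AE and SAE listings. With 6 subjects per GS-248 dose and 8 on celecoxib, one subject visibly changes a percentage.

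The SAP also disagrees with itself. Both disposition shells still count a safety set and a per-protocol set, and the MAD shell counts a PK set, although SAP 4.2 marks all three as not applicable.

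**Working it through.** **1. Scope.** SAP 3.4 gives 48 SAD + 24 MAD + 8 celecoxib = 80, which matches its stated total. The combined outputs cover 24 + 8 = 32 subjects, and 32/80 = 40%. MAD has 3 × 6 = 18 on GS-248 and 3 × 2 = 6 on placebo.

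Safety table shells: 14.2.1.1 and 14.2.1.2 (2), 14.2.3.1 to 14.2.3.3 (3), 14.3.4.1 (1), 14.3.5.1 to 14.3.5.5 (5), 14.3.6.1 and 14.3.6.2 (2), total 13. Safety listings: 16.2.6.1 to 16.2.6.5 (5), 16.2.7, 16.2.8, 16.2.9.1, 16.2.9.2 and 16.2.9, total 10. Together 23 outputs.

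**2. What the FAS condition could mean.**

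| Reading of efficacy data | Consequence for the safety outputs |
|---|---|
| Any post-dose assessment | FAS is in practice all dosed subjects; no effect |
| Any post-dose PD value | A dosed subject with no PD value is excluded |
| An efficacy endpoint, literally | Nobody qualifies, since the trial has none |

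The second is the most natural working reading and is used below. Separately, both set definitions require randomisation, but protocol 9.8 and SAP 3.6 describe Part IV as non-randomised. Read literally, neither set admits any of the 8 celecoxib subjects.

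**3. How likely an exclusion is.** The schedules for MAD (protocol Tables 8.1-3 and 8.1-4) and Part IV (Table 8.1-7) give these PD collections after the first dose:

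- blood: Day 1 at 2, 8 and 24 h (3); Day 10 pre-dose and at 2, 8 and 24 h (4); total 7
- urine: three intervals on Day 1 and three on Day 10; total 6

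All 7 + 6 = 13 would have to yield no value. For a subject who completes the first 24 h and then leaves, the number is 3 + 3 = 6; for one who leaves sooner it is fewer. The first blood sample is due 2 h after dosing, in the clinic.

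**4. Effect if one subject were excluded (an assumption; none is reported).** With no AE in the group, the two-sided 95% Clopper-Pearson upper bound is 1 − 0.025^(1/n). For example, n = 6 gives 1 − 0.025^(1/6) = 45.9%. The last two columns need further assumptions: that the group had exactly one AE subject, and whether the excluded subject was that one.

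| Group | n | Upper bound, 0 events | Only AE was in the excluded subject | Only AE was in another subject |
|---|---|---|---|---|
| One GS-248 dose, or MAD placebo | 6 → 5 | 45.9% → 52.2% | 1/6 (16.7%) → 0/5 | 1/6 (16.7%) → 1/5 (20.0%) |
| Celecoxib | 8 → 7 | 36.9% → 41.0% | 1/8 (12.5%) → 0/7 | 1/8 (12.5%) → 1/7 (14.3%) |
| All GS-248 | 18 → 17 | 18.5% → 19.5% | 1/18 (5.6%) → 0/17 | 1/18 (5.6%) → 1/17 (5.9%) |

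The plan calls for no confidence intervals on AEs; the bounds only show how little slack these groups have.

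**The case against.** The strongest reply is that the two sets will coincide. SAP 3.4 reports full cohorts dosed, subjects were resident for the first samples, and several blood and urine measures could each qualify a subject. SAP 4.7 sets values below detection to half the limit, so a suppressed PGE2 level is not a missing one. This stands, and it is why the practical impact is low.

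The choice of set is also not hidden. SAP 2 and 4.2 both state it, protocol 17.5 assigns no set that the SAP could override, and the efficacy wording comes from protocol 17.3.2. All true. The departure is from a safety set the protocol defines, in a trial whose primary objective is safety, and not from an explicit assignment. It still belongs in SAP 8.

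SAP 4.4 says that, in general, collected data will be listed, and protocol 17.5.1 expects all AE data to be listed. An excluded subject's events might therefore still appear. But the listing titles say FAS, so the SAP conflicts with itself here, and the AE percentages use the analysis set in any case. The disposition counts, Listing 16.2.1 (discontinued subjects), Listing 16.2.3.2 (population definitions) and the discontinuation table in SAP 7.4 would reveal an exclusion only in part.

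Finally, the earlier part-specific SAPs may have handled this, and they cannot be checked here. SAP 9 lists the MAD SAP, the MAD outputs and the Part IV SAP as superseded, so this SAP governs. SAD safety outputs are outside the point.

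**Conclusion.** The concern holds. As written, the denominators for the primary safety outputs of 32 subjects depend on an undefined efficacy value and, read literally, on a randomisation that Part IV never had. The change is missing from SAP 8 and clashes with the disposition shells.

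It should be fixed, but the practical impact is low: zero if every dosed subject has a qualifying value, which is likely and which nothing in the documents contradicts. The shifts in the table are conditional on one excluded subject and on reading efficacy as PD; the AE columns also assume a single event. They do not estimate what happened.

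**What to change.** - In SAP 4.2, define the safety set as all subjects who received at least one dose. Restoring protocol 17.3.1 word for word is not enough, because its randomisation condition does not fit Part IV.
- Use that set for every AE, ECG, vital-sign, laboratory and physical-examination table and listing.
- Keep the FAS for PD outputs and name the variables that qualify a subject, for example whole blood assay PGE2, ADMA/L-arginine and urinary AA metabolites. Word its randomisation condition so that Part IV subjects can enter.
- Enter any remaining departure in SAP 8, and align the disposition shells with the sets actually used.

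Two smaller corrections belong with this. SAP 3.4 describes the Part IV subjects as randomised, against SAP 3.6; protocol 9.3 has the same slip. SAP 4.2 marks the PK set as not applicable although MAD PK shells remain. Any MAD PK analysis output produced under this SAP should use the protocol 17.3.4 set, as protocol 17.6.1 requires. Listing individual PK data on a wider set is less of a problem.

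The cost is SAP wording, listing titles and the population flag in the table programs. No new data are needed.

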Testicular degeneration was noted histopathologically in the 3 male dogs at the highest dose level in the 28-day study that were necropsied pre-terminally on Day 21. These changes were interpreted as most probably being secondary effects as a result of the poor physiological condition of these animals, and therefore not directly related to GS-248 treatment. Furthermore, as no such changes were noted at the NOAEL (the intermediate dose level) in this study, there will be sufficient safety margins to such effects in the present study.

The phototoxicity of GS-248 has not been investigated, but based on the MEC value obtained from absorbance studies and the weak and comparatively short-lived potential binding of radioactivity to melanin-containing tissues of the ocular bulb, a phototoxic potential cannot be excluded. Thus sun protection, as defined in Section 9.5.2, should be used during the study.

The selection of starting-dose and dose-escalation steps represents a careful approach to administer GS-248 for the first time in humans (see Section 8.3). Sentinel dosing will apply for the first 2 subjects in each SAD cohort.

SSc patients participating in the study may experience some symptom relief. The risks for SSc patients are considered to be comparable to those identified for the healthy volunteers participating in Part I and Part II of the study with the exception that patients may experience

discomfort following withdrawal of e.g. proton pump inhibitors (PPIs) and other medications (see below).

In Part I, II and III, use of antacids, PPIs or any medication that changes gastric pH is disallowed from 14 days prior to IMP administration and during the study since GS-248 is a low solubility compound with pH dependent solubility. A high pH may decrease exposure.

Use of NSAIDs, coxibs and aspirin is prohibited from 14 days prior to IMP administration and during the study to avoid interference with the GS-248 signal transduction pathway and evaluation of study results.

The iSRC will monitor emerging safety and PK data over the course of the study and must give a favourable recommendation prior to any dose escalation, see Section 8.3.7 and Section 8.3.8 for stopping criteria for dose escalation and for further information about the iSRC.

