17.6 Analysis of secondary endpoints

17.6.1 Analysis of pharmacokinetics

The PK analysis will be based on the PK analysis set and performed by CTC. The PK parameters will be calculated by non-compartmental analysis (NCA) using the software Phoenix WinNonlin[®] version 6.3 or later (Pharsight Corporation, U.S.A.).

The following non-compartmental PK parameters will be assessed in Part I (SAD):

- AUC_{0-t} ,
- $AUC_{0-\infty}$,
- $T_{1/2}$,
- T_{max} ,
- C_{max} ,
- Dose proportionality after a single dose based on AUC and C_{max}
- V_z/F
- CL/F

The following non-compartmental PK parameters will be assessed after the first dose interval in Part II (MAD) and Part III (SSc patients):

- AUC_{0-t}
- $T_{1/2}$
- T_{max}
- C_{max}
- Dose proportionality after the first dose interval based on AUC and C_{max}

The following non-compartmental PK parameters will be assessed after the last dose interval in Part II (MAD) and Part III (SSc patients):

- AUC_{0-t}
- AUC_{ss}
- $T_{1/2}$
- T_{max}
- C_{max}
- C_{trough} from the 2 doses preceding the last dose
- Dose proportionality after the last dose interval based on AUC_{ss} and C_{max}
- V_z/F
- CL/F
- Accumulation ratio

Summary statistics for the PK parameters will be presented by part, treatment and cohort with number of measurements, arithmetic mean, SD, CV, median, minimum, maximum, geometric mean, geometric CV%. Additional PK parameters may be determined if deemed appropriate.

All data will be listed by part, cohort, treatment and subject/patient.

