17.7 Analysis of exploratory endpoints

17.7.1 *Analysis of mPGES-1 activity (PGE₂ levels) levels using whole blood assay*

PGE₂ levels will be summarised by part, treatment and cohort with absolute and percent change from baseline at each visit.

All data will be listed by part, cohort, treatment and subject/patient.

17.7.2 *ADMA and AA metabolites in plasma and urine*

Each parameter will be summarised by part, treatment and cohort with absolute and percent change from baseline at each visit.

All data will be listed by part, cohort, treatment and subject/patient.

17.7.3 *Metabolites in safety testing (MIST)*

Details will be specified elsewhere.

17.7.4 *Future exploratory analyses of biomarkers and GS-248 metabolites*

Details will be specified elsewhere.

17.7.5 *Raynaud's questioning*

Data will be listed by treatment and patient.

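### For Part II (MAD) PK, SAP 4.2 replaces the protocol's PK analysis set with the FAS, does not declare the change, and contradicts itself on the point

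*SAP*

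**What the plan says.** **Protocol.** Section 17.3.4 defines a PK analysis set of dosed subjects with evaluable concentration data "who have no AEs or protocol deviations judged to affect the PK analysis". Section 17.6.1 puts it to use: "The PK analysis will be based on the PK analysis set and performed by CTC". Section 17.3.3 also defines a per-protocol set of randomised subjects who "completed the study without any major protocol deviations that are judged to compromise the analysis of the data", but Section 17 ties no analysis to it. On whole-blood PGE2, Section 17.7.1 says that "levels will be summarised by part, treatment and cohort with absolute and percent change from baseline at each visit" and names no set. Section 17.7.2, on ADMA and the urinary metabolites, names none either.

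**SAP.** Section 4.2 defines the FAS and enters the safety, per-protocol and PK sets as not applicable. It then says: "The FAS population will be used for all analyses presented in this SAP". The next sentence reads: "Safety analysis set and Per protocol analysis set (PPS) will not be used in any part or in any analysis". That sentence does not mention the PK set. Section 4.8 plans one sensitivity approach, for exploratory endpoints only: all data against subjects with complete data. Section 8 records changes from the protocol, and none of them concerns analysis sets.

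**The concern.** The protocol gives PK its own set so that a subject with compromised exposure data does not enter the dose-group summaries. If MAD PK is summarised on the FAS, the plan has no step that removes such a subject. The outputs at stake are the MAD PK parameters (including AUCss and Cmax), the concentration summaries, and the dose-proportionality tables and figures. Each dose group has six subjects, so each one carries 1/6 (16.7%) of a group mean.

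The change is also undeclared. Someone comparing the report with the protocol would expect the PK set and would find nothing in Section 8 to say otherwise. A programmer working from the SAP would find contradictory instructions.

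**Working it through.** **Step 1. Does the SAP cover MAD PK?** The evidence, set side by side:

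- *Suggesting it does not:* Section 3.1 labels the secondary endpoints as included in previous SAPs. Section 7.2 says they have already been estimated for Parts I and II under those SAPs. Section 7 gives no PK method.
- *Suggesting it does:* Section 9 lists the MAD SAP and the MAD tables, listings and figures as superseded by this version. Section 2 puts the descriptive tables on the FAS. Section 10 says that PK parameters will be calculated by non-compartmental analysis. Section 13 contains MAD shells for PK parameters (Table 14.3.1.x), concentrations (Table 14.3.2.x), dose proportionality (Figures 14.3.3.1.x and 14.3.3.2.x, Table 14.3.3.3.1) and concentration plots (Figure 14.3.4.x).

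With the MAD SAP and its outputs superseded, this SAP is the operative one for MAD PK.

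**Step 2. Which set would be used?** Section 4.2 says the FAS, and so do Listings 16.2.10.1 (concentrations) and 16.2.10.3 (PK parameters). The PK table shells leave the set as a placeholder. The MAD disposition shell (Table 14.1.2.1) still counts subjects in the per-protocol and PK sets, and Listing 16.2.3.1 still lists exclusions from the per-protocol set, although Section 4.2 calls both sets not applicable.

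**Step 3. What is outside this?** Section 2 uses Part I data only for exploratory endpoints, and Section 9 does not mark the SAD SAP or its outputs as superseded. Part I PK is therefore not affected here. For PD, the protocol assigns no set, so there is nothing to depart from.

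**Step 4. Size.** The plan states no figure on this point to reproduce. The head count in SAP 3.4 adds up: 6×8 + 3×8 + 8 = 80. MAD has 6 subjects per dose and 3×2 = 6 pooled placebo.

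Assume five subjects with equal exposure and a sixth at a fraction f of it. The relative change is f^(1/6) − 1 for the geometric mean and (5 + f)/6 − 1 for the arithmetic mean.

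| f | Geometric mean | Arithmetic mean |
|---|---|---|
| 0.10 | −31.9% | −15.0% |
| 0.25 | −20.6% | −12.5% |
| 0.50 | −10.9% | −8.3% |
| 0.75 | −4.7% | −4.2% |

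If that subject is excluded, the shift is zero.

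**Step 5. The PD tests, for the optional part of the fix.** These are exact two-sided Wilcoxon tests (the SAP sets 5% without stating sides), 6 against 6, with C(12,6) = 924 arrangements.

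- Complete separation: 2/924 = 0.0022.
- One subject ranked beyond the whole opposite group (U = 6): 60/924 = 0.065. With that subject removed, 5 against 6: 2/462 = 0.0043.
- One placebo subject ranked in the middle of the actives (U = 3): 14/924 = 0.015.
- One active subject misranked at the extreme against celecoxib (n = 8): 0.043 retained, 0.0016 excluded.
- The same against all placebo from SAD cohorts 3 to 6 plus MAD (n = 8 + 6 = 14): 0.020 retained, 0.0002 excluded.

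**The case against.** The strongest reply is that the not-applicable entry for the PK set means only that PK is not re-analysed in this document. Section 7.2 supports that. So do the lack of a PK method in Section 7, the unfilled placeholders, and the sentence barring other sets, which names the safety and per-protocol sets but not the PK set. The MAD SAP is not among the documents and may have applied the PK set. This leaves the sponsor's intention open. It does not remove the problem, because the SAP declares that MAD SAP superseded, carries the PK shells itself and puts the PK listings on the FAS.

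It is also fair that one subject's influence can be traced by hand: the listings cover deviations, exposure and individual PK parameters, and Table 14.3.3.3.1 prints individual values. The planned summaries would still include that subject.

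A reader might infer several stronger things that the documents do not support:

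- *Every PK mean in the study is affected.* Part I PK lies outside this SAP. Nor does the Table 14.3.1.x footnote list the accumulation ratio.
- *The PGE2 and urine tests breach the protocol.* No set is assigned to them, and the FAS is a defensible choice for exploratory PD.
- *Subjects who vomited, missed doses or took an NSAID will be retained.* No document shows that such a subject exists. Exclusion under the protocol is by judgement and names none of these events. MAD doses are given in the clinic under supervision (Protocol 10.8), and NSAID use is not shown to alter GS-248 PK.
- *One deviator overturns the PD result.* Only the worst-case rank, 6 against 6, crosses 5%. The other cases in Step 5 do not, and SAP 3.3 states no hypotheses.

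**Conclusion.** The point holds for MAD PK. Section 4.2 as written conflicts with Protocol 17.6.1, Section 8 does not declare the change, and Sections 4.2, 7.2, 9 and 13 of the SAP cannot all be followed together.

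The numerical effect is unknown and may be nil. It is nil if no AE or deviation was judged to affect PK, because then no exclusion on that ground separates the two sets. The 32%, 21% and 11% reductions assume exactly one affected subject in six, with exposure at 10%, 25% or 50% of five equal values; they are not trial data.

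For PD there is no departure from the protocol. What is absent is a sensitivity analysis without deviators, since the complete-data version in Section 4.8 keeps a deviator whose data are complete. Adding one is optional.

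**What to change.** **Needed.** In SAP 4.2, restore the Protocol 17.3.4 PK analysis set for the MAD PK outputs: Tables 14.3.1.x, 14.3.2.x and 14.3.3.3.1, and Figures 14.3.3.1.x, 14.3.3.2.x and 14.3.4.x. Base exclusions on the deviation classifications that Protocol 17.3.3 requires before database lock. SAP 3.6 says that allocation was disclosed only after each part was locked, so these should exist from before unblinding. Fill the analysis-set placeholders to match, make Section 7.2 and the disposition and exclusion outputs agree with Section 4.2, and declare any remaining departure in Section 8.

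**Optional.** Keep the FAS for the main PD tests and repeat the PGE2 and urine tables without major deviators. The protocol's reason for banning NSAIDs, coxibs and aspirin, "to avoid interference with the GS-248 signal transduction pathway and evaluation of study results", makes this a natural check, and celecoxib is partly self-administered at home. Define that set for Part IV by treatment received: the protocol's per-protocol definition requires randomisation and Part IV was not randomised, so a literal reading would drop the celecoxib group. Any deviation not judged before lock should be classified without sight of the PD values.

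**Cost.** SAP wording and one rerun of existing programs. The optional part adds one further set of tables and any outstanding classification work.
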